8.1.2.3. Analysis of other Secondary Endpoints

1. T cell immune response

The number of antigen-specific T cells (expressed as SFC/million PBMC) for each prostate cancer antigen (or antigenic sub region) will be compared between pre-treatment and subsequent post treatment time points in two rounds of analysis. The first round (Cycle 1 analysis) will compare the pretreatment response (Cycle 1 Day 1) to Cycle 1 Day 15, Cycle 1 Day 29, Cycle 1 Day 43 and Cycle 1 Day 71; the second round (Cycle 2 analyses) will compare Cycle 2 Day 1 with remaining timepoints as Cycle 2 Day 29 and Cycle 2 Day 99, or End of Treatment, and Cycle 1 Day 1). Data from the maintenance period may be analyzed in the same manner if deemed necessary. As appropriate, analysis of the immune response endpoints will include fold-change from baseline by patient and fold-change in geometric mean (GMFR) by cohort (by Cycle). The immune response against each peptide pool (5 values: 1 for PSA, 1 for PSCA and 3 for PSMA) may be analyzed separately or per antigen (eg 3 PSMA summed) or all pooled to provide the overall T cell response to the selected prostate cancer antigens.

In case there is failure for Cycle 1 Day 1, the Screening sample would be used as the pretreatment sample.

- Number of treatment-induced immune responses against the prostate cancer antigens will be defined as the number of patients with an X-fold (eg, where X could be defined as 2-fold, 4-fold) increase in at least Y sampling time points (eg, Y=one time, Y=two timepoints) after treatment as compared to the Cycle 1 Day 1 (or Screening/Baseline sample if failure for Cycle 1 Day 1) for the same patient.
- Negative (media only) and positive (anti-CD3) control responses, as well as specific T cell responses observed to CMV, EBV, Flu and Tetanus Toxoid (CEFT) will be reported in a similar manner to the prostate cancer antigen data (ie, in two rounds of analysis).

2. **Antibody response specific to the PSMA antigen (Geometric Mean and Seroconversion)**

The LLOQ for the assay will be provided by the testing labs. Titers below the assay detection limit will be assigned a value of one-half that limit.

Geometric Mean Titer: For the analyses on antibody titer, least squares (ie, estimated) Geometric mean titer (GMT) will be calculated at baseline and post baseline. All statistical analyses will be performed on the logarithmically (natural base) transformed titer values. See [10.1](#).

Geometric Mean Fold Rise: The least squares (ie, estimated) GMFR of the post-vaccination titer value to the previous titer level (other than at baseline) will be calculated, as well as the associated confidence interval and the median, minimal, and maximal n-fold increase. See [10.1](#).

Seroconversion: Number of patients from negative to positive (eg, k fold above the assay detection) or with at least an X-fold increase from baseline (eg, k=2,3; X=2,4).

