### **3.1.2. Dose Expansion (Part B)**

In Part B, the selected doses of the PrCa VBIR in combinations with PF-06801591 were evaluated in two populations: (1) Participants with mCRPC whose disease has progressed despite novel hormone therapy (abiraterone or enzalutamide) to be treated with PrCa VBIR+ PF-06801591 alone; and (2) Participants with biochemical relapse of disease (BCR) to be treated with PrCa VBIR+ PF-06801591.

The study design has changed in two aspects: (1) in the removal of Cohort 10B, because studies of progression on novel-hormone therapy with abiraterone, with a switch to enzalutamide + Pr Ca VBIR, are no longer useful in defining Proof of Concept for this study; and (2) in no longer expanding cohort 3B, because sufficient sample size has been reached to make decisions about further development based upon safety and preliminary efficacy.

The following listing identifies the Expansion Cohorts for Part B:

- Cohort 1B (20 participants treated): Twenty participants with BCR have been enrolled and treated in this expansion cohort, using PrCa VBIR and tremelimumab at a dose level of 80 mg. No PF-06801591 was included in this regimen. **No additional participants will be enrolled.**
- Cohort 5B (15 participants treated): Fifteen participants with BCR and no prior therapy have been treated with PrCa VBIR in combination with 130 mg PF-06801591. **No additional participants will be enrolled.**
- Cohort 3B (18 participants treated): Eighteen participants with mCRPC whose disease has progressed despite novel hormonal treatment (enzalutamide or abiraterone) have been treated with PrCaVBIR in combination with 300 mg PF-06801591. **No additional participants will be enrolled.**

Different cohorts of patients opened for enrollment in parallel. Cohorts are non-randomized; slot assignments were managed by the study team with sites notified in advance of cohort availability. Participants are not allowed to crossover between the different combinations evaluated in this study.

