10. APPENDICES

10.1. Appendix: Statistical Methods for Immunogenicity (serology)

Definitions:

Let x_i , $i=1, 2, n$, be the titer for subject i where n is the number of subjects. Then the geometric mean titer (GMT) is defined as follows

$$\text{GMT} = \exp[(1/n)\sum \log(x_i)],$$

where \log is the natural logarithm.

Within each vaccine group and for each antibody, geometric mean titers (GMTs) will be calculated. Each titer will be logarithmically transformed for analysis. Two (2)-sided, 80% confidence intervals will be constructed by back transformation of the confidence intervals for the mean of the logarithmically transformed assay results.

Let x_i , $i=1, 2, n$, be the titer for test group and let y_i , $i=1, 2, m$, be the titer for reference group. Then the geometric mean ratio (GMR) is defined as follows:

$$\text{GMR} = \exp[(1/n)\sum \log(x_i) - (1/m)\sum \log(y_i)].$$

Also for the GMRs, the confidence intervals will be constructed by back transformation of the confidence intervals for the mean difference of the logarithmically transformed assay results (*test* relative to *reference*).

Let x_i , $i=1, 2, n$, be the titer prior vaccination and let y_i , $i=1, 2, n$, be the titer post vaccination. Then the geometric mean fold rise (GMFR) is defined as follows:

$$\text{GMFR} = \exp[(1/n)\sum \log(y_i/x_i)].$$

For the geometric mean fold rise, the confidence intervals will be constructed by back transformation of the confidence intervals for the mean difference of the logarithmically transformed assay results (*post* to *prior*).

GMTs, GMRs and GMFR will be estimated by an ANCOVA model with natural log transformed anti-body titer as outcome variable, and treatment group as factor and baseline (in log scale) as covariates at each of the post-dose measurement. These analyses based on log-transformed data, the LSMEAN estimates and confidence interval will be back-transformed (exponentiated) and presented. The estimated treatment difference and corresponding confidence intervals from the model will also be back-transformed.

-For GMTs the variable of interest, that will be back transformed, is $\log(x_i)$

x_i , $i=1, 2, n$, be the titer for subject i

-For GMFRs the variable of interest, that will be back transformed, is $\log(y_i) - \log(x_i)$

x_i , $i=1, 2, n$, be the titer prior vaccination and let y_i , $i=1, 2, n$, be the titer post vaccination

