Back-transformation of estimated difference in GMTs (with contrasts) is interpreted as GMR between treatment and placebo group.

In addition to the adjusted analysis for GMTs, GMRs and GMFRs between groups through analysis of covariance, unadjusted (crude) GMTs, GMRs and GMFRs will be calculated as a sensitivity analysis.

For GMTs, two (2)-sided, 80% confidence intervals will be constructed by back transformation of the confidence intervals for the mean of the logarithmically transformed assay results computed using the Student t distribution.

For the GMRs, the confidence intervals will be constructed by back transformation of the confidence intervals for the mean difference of the logarithmically transformed assay results (*test* relative to *reference*) computed using the Student t distribution.

For reporting purposes, 1 decimal place will be used for geometric mean titers (GMTs), and 2 decimal will be used for geometric mean ratios (GMFRs, GMRs).

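### The antibody fold rise is tied to the previous titer with an unclear baseline rule, and Appendix 10.1 makes a between-group model, read against a placebo group that does not exist, the main estimate

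*SAP*

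**What the plan says.** SAP 8.1.2.3, under the antibody heading, plans three summaries.

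- A least-squares "Geometric mean titer (GMT) will be calculated at baseline and post baseline".
- A least-squares fold rise: the "GMFR of the post-vaccination titer value to the previous titer level (other than at baseline) will be calculated", with a pointer to Appendix 10.1.
- Seroconversion: a change from negative to positive, or a rise of at least a set multiple of the baseline titer (2 and 4 are the examples).

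Appendix 10.1 gives the formula ("Then the geometric mean fold rise (GMFR) is defined as follows") as the exponential of the mean of log(y/x), where x is the titer before vaccination and y the titer after. It does not say whether x is taken before the first vaccination or before each one.

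The same appendix says that GMTs, GMRs and GMFRs are "estimated by an ANCOVA model with natural log transformed anti-body titer as outcome variable, and treatment group as factor", with log baseline as covariate, at each post-dose measurement. The back-transformed contrast "is interpreted as GMR between treatment and placebo group". Unadjusted values are a sensitivity analysis, and the stated intervals are two-sided 80%.

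Protocol 3.1.2 states: "Cohorts are non-randomized; slot assignments were managed by the study team". Protocol 5.1 describes open-label treatment. Protocol 9.6.2 plans only n, median, minimum and maximum for antibody titers by cohort and time. SAP 4.1 rules out formal hypothesis tests.

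**The concern.** The regimen vaccinates repeatedly: an adenovirus prime and three DNA boosts per cycle, two cycles, then maintenance boosts (Protocol 3.1 and 3.1.3). The titer before vaccination is therefore a different number at each dose, and the choice of denominator changes what the fold rise measures. Against the previous titer it measures the latest step; against baseline it measures the response so far. The text in 8.1.2.3 names the former, qualifies it with a parenthesis that can be read two ways, and points to an appendix that does not settle it. Two programmers could produce different tables from the same SAP.

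The model raises a separate problem. A contrast labelled treatment against placebo invites a causal reading that the design cannot give. An adjusted GMT also describes a cohort at a baseline titer that the cohort did not have. Antibody response is listed among the Part A secondary endpoints in SAP 6.2, so these tables will be reported as evidence of vaccine activity.

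**Working it through.** The documents give no titers, effect size or power for this analysis, so there is no stated figure to reproduce. The titer paths, slopes and standard deviations below are assumptions. The formula and model are from Appendix 10.1, and the group sizes 20 and 15 are those of Cohorts 1B and 5B (Protocol 3.1.2).

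**Step 1. Fold rise.** GMFR = exp[(1/n) Σ log(y/x)]. If all patients share one path, this reduces to y/x.

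| Assumed titers, baseline first | x = previous titer | x = baseline |
|---|---|---|
| 10, 80, 80, 80 (sustained) | 8, 1, 1 | 8, 8, 8 |
| 10, 160, 80, 40, 40 (waning) | 16, 0.5, 0.5, 1 | 16, 8, 4, 4 |
| 10, 20, 40, 80, 160 (stepwise) | 2, 2, 2, 2 | 2, 4, 8, 16 |

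If the parenthesis means every visit except baseline itself, the middle column stands. If it means that baseline is never a denominator, the first ratio drops out and the sustained path shows only 1, 1.

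On the sustained path the other planned summaries are unaffected. The GMT reads 80 against 10, and 80/10 = 8 passes both the 2-fold and the 4-fold seroconversion examples at every visit.

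**Step 2. Comparator.** Every cohort listed in Protocol 1.3.2 and 3.1.2 receives active components, so no group fits the placebo label. The test and reference groups of the GMR formula are never assigned. *Treatment group* is not defined as cohort. Cohort is the natural reading, because SAP 8 summarises by cohort and 8.1.2.1 equates dose with cohort. Cohorts 1B and 5B are biochemical relapse and 3B is mCRPC. Cohort 1B receives no PF-06801591; 5B and 3B receive it at different doses.

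**Step 3. Shift of the adjusted GMT.** With slope β on log baseline, and least-squares means taken at the pooled mean baseline (the usual default; the SAP does not state it), adjusted GMT ÷ crude GMT = exp[β × (pooled mean log baseline − cohort mean log baseline)]. For a cohort 1 natural-log unit below the pooled mean (a 2.72-fold lower baseline titer):

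- β = 0.5: exp(0.5) = 1.65
- β = 0.8: exp(0.8) = 2.23
- β = 1.0: exp(1.0) = 2.72

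A cohort above the mean is divided by the same factor. With equal baselines the factor is exp(0) = 1.

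A simulation with groups of 20 and 15, log-scale SD 1, slope 0.5 and no true group effect agrees. With equal baselines, the adjusted and crude GMTs of the second group are 54.1 and 54.2. With the second group's baseline 1 log unit higher than the first's, they are 67.2 and 88.9, a ratio of 88.9/67.2 = 1.32. By formula, the second group lies 20/35 = 0.571 above the pooled mean, and exp(0.5 × 0.571) = 1.33.

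**Step 4. Baseline GMT.** Section 8.1.2.3 asks for a least-squares GMT at baseline. Regressing log baseline on group and log baseline gives coefficients 0 (intercept), 0 (group) and 1 (baseline). The fit is exact, and every group's least-squares mean equals the pooled baseline. Appendix 10.1 specifies the model only for post-dose measurements, so the baseline estimate that 8.1.2.3 requests has no usable model.

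**The case against.** A reader might infer that a sustained antibody response would be reported as no response. The documents do not support that. It is true of the GMFR alone: GMT by visit, baseline-referenced seroconversion and the protocol's descriptive titers would all show the response. SAP 8.1.2.3 also says that "analysis of the immune response endpoints will include fold-change from baseline by patient", although that sentence stands under the T cell heading and is qualified as applying where appropriate.

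A reader might also infer that there is no valid comparator at all. Between groups there is no randomised or placebo comparator, but each patient's own baseline is one, and seroconversion uses it.

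Nor is an outright conflict between 8.1.2.3 and 10.1 established, since the appendix wording fits either denominator. In a prime-boost regimen the ratio to the previous titer is itself a legitimate measure of boosting. Treatment group need not mean cohort: 3A and 1B share a regimen, as do 6A and 5B (Protocol 1.3.2). Crude estimates are already planned, with Student t intervals for the GMT, and no test or decision rule depends on which set is called main.

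These points limit the consequences. They do not supply a reference visit for the fold rise, a placebo group, or a reason to prefer a between-group model in a study whose protocol plans description by cohort. Any single figure for the adjusted-GMT shift would rest on one assumed case, so only a range can be given.

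**Conclusion.** The point holds in limited form. The antibody GMFR is referenced to the previous titer under an ambiguous rule. On that reading it falls to 1 once a rise is sustained, where a baseline reference would keep showing the full rise (8 in the assumed example). The placebo interpretation is wrong on any reading. If treatment group means cohort, the main estimates adjust non-randomised cohorts with different populations and regimens to a common baseline. That changes a GMT by a factor of about 1.6 to 2.7 for a cohort 1 natural-log unit from the pooled mean and slopes of 0.5 to 1.0, by less when baselines are closer, and not at all when they are equal. The least-squares GMT at baseline cannot be produced from the stated model.

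The titers, slopes and baseline distances are assumptions. The endpoint is secondary and descriptive, no hypothesis is tested, and other planned summaries would still reveal a response. The correction is worth making but is not critical.

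**What to change.** In SAP 8.1.2.3, define the antibody GMFR at each visit against Cycle 1 Day 1, using the Screening sample if that one fails, as the SAP already does for T cells. Keep the ratio to the previous titer, if wanted, as a supplementary measure of boosting, and name the visits that it compares.

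In Appendix 10.1, state the same reference in the formula. Make unadjusted within-cohort GMT and GMFR with t-based intervals the main summary, including the GMT at baseline. Delete the placebo sentence. If any between-cohort ratio is kept, define the groups and label it as descriptive and non-randomised.

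The cost is SAP wording, and the programming becomes simpler. No data collection changes.

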6.2. Part A Secondary Endpoint

- *Immune response including T cells specific to the three selected prostate cancer tumor-antigens. T cell immune response will be determined as the frequency of IFN- γ spot forming cells (SFC)/million peripheral blood mononuclear cells (PBMC) in response to Prostate-Specific Membrane Antigen (PSMA), Prostate Stem Cell Antigen (PSCA) and Prostate-Specific Antigen (PSA) as measured in the IFN- γ ELISPOT assay. For analysis in the IFN- γ ELISPOT assay, the PSMA antigen will*

[figure not shown]
be divided into three sub regions (peptide pools) for which the IFN- γ spot forming cells/million PBMCs will be reported separately (ie, 5 reported values) or by antigen (3 PSMA summed) or all pooled. The PSCA and PSA assays will each be analyzed as a single antigen (ie, 1 reported value for each antigen). ELISPOT assay reported variables, by the Lab, are specified and listed in the respective CSAP document.

- *Antibody response specific to the PSMA antigen* (Geometric Means and Seroconversion): will be determined as the titer (U/mL) of serum IgG antibodies elicited against the PSMA antigen as measured in the Luminex-based assay.
- *Laboratory abnormalities as characterized by type, frequency, severity (as graded by NCI CTCAE v 4.03) and timing.*
- *Tremelimumab single-dose PK parameters, including the maximum concentration (C_{max}), time to maximum concentration (T_{max}), and area under the concentration versus time curve (AUC) from time zero to the last quantifiable time point prior to the second tremelimumab dose (AUC_{last}) and if data permit, AUC from time zero extrapolated to infinity (AUC_{0-inf}); and trough concentrations after multiple dosing (C_{trough}).*
- *PF-06801591 single-dose PK parameters, including C_{max} , T_{max} , AUC_{last} , and if data permit, AUC_{inf} , and C_{trough} after multiple dosing.*
- *Incidence and titers of ADA and neutralizing antibodies against tremelimumab.*
- *Incidence and titers of ADA and neutralizing antibodies against PF-06801591.*

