7.2. Immune Responses Lower Limit of Quantitation

Titers below the assay detection limit will be assigned a value of one-half that limit.

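### For an undetectable baseline titer, the half-limit value plus an unrestricted X-fold arm leaves the k-fold positivity cut-off without effect, and at X=2 a reading at the detection limit counts as seroconversion

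*SAP*

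**What the plan says.** SAP 6.2 lists the PSMA antibody response as a Part A secondary endpoint, which "will be determined as the titer (U/mL) of serum IgG antibodies elicited against the PSMA antigen as measured in the Luminex-based assay". It is to be summarised by geometric means and by seroconversion.

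SAP 7.2 gives the rule for low readings, and SAP 8.1.2.3 repeats it: "Titers below the assay detection limit will be assigned a value of one-half that limit". On the quantitation limit, SAP 8.1.2.3 says only that "The LLOQ for the assay will be provided by the testing labs". It does not say how that limit relates to the detection limit.

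The count is then defined in SAP 8.1.2.3 as "Seroconversion: Number of patients from negative to positive", with the detail "eg, k fold above the assay detection) or with at least an X-fold increase from baseline (eg, k=2,3; X=2,4". Three things are left open:
- Negative has no definition of its own.
- k and X are examples, not chosen values.
- The fold arm is not limited to participants whose baseline was detectable.

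For T cells, the responder rule in the same section requires "an X-fold (eg, where X could be defined as 2-fold, 4-fold) increase in at least Y sampling time points", and Y is likewise given only by example, as one or two.

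**The concern.** The positivity arm exists so that a participant who starts negative must show a reading clearly above the detection limit, two or three times above it, before being called a seroconverter. The fold arm starts from an imputed value that is itself half the limit. A rise that is large on the ratio scale may therefore be only a move from just under the limit to the limit itself. With the arms joined by an or, the looser one decides.

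Immune response to the vaccine antigens is the first Part A secondary objective. The cohorts have no concurrent untreated control, so no comparison within the study would separate readings that drift across the limit from a real antibody response. SAP section 3 also notes that the study is open label and that the sponsor's team reviews immunogenicity data throughout. The choice among the example values of k and X could therefore be made with the data in view.

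**Working it through.** **Inputs from the documents.** Undetectable titers are set to L/2 (SAP 7.2 and 8.1.2.3). k is 2 or 3 and X is 2 or 4, joined by an or (SAP 8.1.2.3). The documents state no seroconversion rate, so there is no figure of theirs to reproduce.

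**Step 1: threshold for an undetectable baseline.** The fold arm is met at X × L/2 and the positivity arm at k × L. Under the or, the lowest reading that counts is min(kL, X·L/2).

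| X | k | Fold arm | Positivity arm | Lowest reading counted | Role of k |
|---|---|---|---|---|---|
| 2 | 2 | L | 2L | L | bypassed |
| 2 | 3 | L | 3L | L | bypassed |
| 4 | 2 | 2L | 2L | 2L | coincides |
| 4 | 3 | 2L | 3L | 2L | bypassed |

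Since X/2 ≤ k in every row, k never adds a requirement. At X=2 the threshold is L.

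**Step 2: threshold for a detectable baseline b.** The fold arm is met at X·b. If negative means below kL, the positivity arm can decide here. With X=4, k=2 and b=1.5L, it is met at 2L and the fold arm at 6L. With X=2, k=3 and b=1.9L, the values are 3L and 3.8L. So k loses its effect for undetectable baselines, not for everyone.

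**Step 3: size of the noise effect, on assumed inputs.** The documents give no assay CV, no titer distribution and no list of serology draws for this count. Assume lognormal assay error with CV 25%, so the SD of ln(titer) is s = √ln(1 + 0.25²) = 0.246. Also assume an undetectable baseline, a constant true median titer m, and 7 independent post-dose draws. One draw reaches threshold T with probability p = 1 − Φ(ln(T/m)/s). At least one of seven does so with probability 1 − (1 − p)⁷.

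| True titer m | p at T = L (X=2) | Any of 7 at L | Any of 7 at 2L |
|---|---|---|---|
| 0.5L | 0.0024 | 1.7% | below 0.1% |
| 0.7L | 0.074 | 41% | below 0.1% |
| 0.8L | 0.182 | 76% | 0.1% |
| 0.9L | 0.334 | 94% | 0.4% |

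With 4 draws in place of 7, the X=2 figures for 0.7L and 0.9L are 26% and 80%.

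**Step 4: after the repair.** If an undetectable baseline must reach kL, the threshold is 2L or 3L, which is 4-fold or 6-fold over the imputed L/2. The last column above then applies for k=2. For k=3 every entry is below 0.1%. A reading at L never counts.

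**The case against.** **A narrower reading of the rule.** The sentence could be meant as negative-to-positive for participants who start negative and a fold rise for the rest. On that reading the problem disappears. The SAP does not say so, and a programmer following the text would apply the fold arm to all participants. The objection supports the repair rather than removing the need for it.

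**X=4 already avoids the worst case.** This stands. With X=4 the threshold is 2L, and the false rate under the same assumptions is at most 0.4%. A reader might infer that any reading at the limit counts under the rule as a whole. That holds only at X=2. With X=4 it would need a lowest reportable value of at least twice the detection limit, and the documents do not give that ratio. Nor is k without effect throughout, as step 2 shows.

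**The large percentages rest on chosen inputs.** This also stands. The 41% to 94% range places participants at 0.7L to 0.9L. At 0.5L the rate is about 2%, and at 0.4L it is under 0.1%. Nothing in the documents says where baseline-negative participants lie.

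**Limited impact.** SAP 4.1 plans no hypothesis test, and protocol 9.6.2 plans descriptive titer summaries without naming a seroconversion count. Geometric means, fold rises with intervals, and median, minimum and maximum fold increases are reported alongside and would help to expose trivial rises. This bears on priority, not on whether the rule is sound.

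**T cells.** A reader might extend the same finding to the ELISPOT responder rule. The documents do not support that. The half-limit value is worded for titers, and there is no k arm to bypass. SAP 6.2 also refers ELISPOT reported variables to a separate CSAP that was not available here and may contain a positivity floor. Nor does the SAP define a responder as positive in any one of the five peptide pools, so a false-positive rate on that basis would describe an endpoint that is not planned.

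**Conclusion.** The point holds for participants with an undetectable baseline titer. For them the effective threshold is L at X=2 and 2L at X=4. The k cut-off is bypassed in three of the four listed combinations and coincides with the fold arm in the fourth. At X=2 a reading at the detection limit is counted as seroconversion, although the positivity arm would not call it positive. This part follows from the SAP's own wording and needs no assay assumption beyond reading the or literally.

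The number of false counts is uncertain. On the assumptions in step 3 it runs from about 2% to 94% at X=2, according to where the true titers lie below the limit. The consequence is confined to a descriptive secondary count. It is still worth correcting, because the stated rule can produce a wrong number. This is more than a missing detail.

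**What to change.** In SAP 8.1.2.3:

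1. State that a participant with an undetectable baseline seroconverts only if a post-dose titer reaches k × L.
2. State that the X-fold arm applies only to participants with a detectable baseline.
3. Fix one k and one X before analysis, and show the other listed values as sensitivity analyses.
4. Define negative, and say how the detection limit relates to the LLOQ supplied by the laboratories.

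As a secondary matter for the T-cell rule, fix X, Y and the pooling level in advance, and cite from the CSAP any positivity floor that it contains.

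The cost is a few sentences of SAP text and a small programming change, with no new data or samples. The downside is that reported seroconversion counts may be lower.
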